## 4 Study Design

---

This is a prospective, subject masked; bilateral, 4-week refit study comparing the fitting characteristics of Clariti Elite sphere lenses, (somofilcon A), against Avaira Vitality silicone hydrogel sphere lenses (fanfilcon A). A total of 40 subjects will be enrolled with the aim of completing 34.

Subject's will be evaluated at the first visit and then fitted with both study lenses to confirm lens fit and optimize visual acuity if needed. At the second visit, the first pair of study lenses, (e.g. somofilcon A), will be dispensed and worn for 4-weeks. After 4-weeks of daily wear with the first pair, subjects will return for a third evaluation and then fitted with the second pair, (e.g. fanfilcon A), of study lenses for 4-weeks. A fourth visit will be scheduled after 2-weeks of lens wear. A fifth and final visit will be scheduled after 4-week of lens wear. The study timeline is shown in Appendix 2.

## 5 Investigational Sites

---

### 5.1 Number of Sites

---

This will be a single-center investigational site in Mexico City. (Target 40 subjects, complete 34).

### 5.2 Investigator Recruitment

---

This study will be conducted at the National Autonomous University of Mexico. [name]. The Investigators will be required to fulfil the following criteria:

- Licensed Optometrist with at least two years of contact lens fitting experience.
- Experienced Investigators who will be trained in Good Clinical Practice (GCP) by the principal investigator.
- In-office email or fax.
- Willingness to follow the study protocol and to co-operate with the study monitors.

This clinical study is designed to be in conformance with the ethical principles in the Declaration of Helsinki, with the ICH guidelines for Good Clinical Practice (GCP) and all the applicable local guidelines.

## **6 Ethics Review / Statement of Compliance**

---

### **6.1 Relevant Standards / Guidelines**

---

This implementation document has been developed in accordance with the following:

- ISO 14155 Clinical Investigation of Medical Devices for Human Subjects, Parts 1 & 2, 2011.
- ICH Harmonized Tripartite Guideline for Good Clinical Practice E6, 1996.
- Declaration of Helsinki
- COFEPRIS Applicable Guidelines

### **6.2 Institutional Review Board**

---

This study will be conducted in accordance with Institutional Review Board regulations (U.S. 21CFR Part 56.103) or applicable IEC regulations. Copies of all IRB/IEC correspondence with the investigator/sponsor will be kept on file. The study will commence upon approval from the following Ethics Committee: Comisión de Ética de la FESI. [name]. [contact] and email address [contact].

### **6.3 Clinical Trial Registration**

---

This study will be registered with clinicaltrials.gov in accordance with section 801 of the Food and Drug Administration (FDA) Act which mandates the registration of certain clinical trials of drugs and medical devices.

### **6.4 Informed Consent**

---

Informed consent shall be obtained in writing from the subject and the process shall be documented before any procedure specific to the clinical investigation is carried out.

## **7 Potential Risks and Benefits to Human Subjects**

---

There may be direct benefits to the subjects in this study such as improved vision, comfort, convenience, and cosmetic advantage. Participation in a study may contribute to scientific research information that may be used in the development of new contact lens products. In addition, subjects will receive an examination of the front part of their eyes and may have the opportunity to try a different type of soft contact lenses and/or different lens care products at

no cost to them. The contact lens materials used in this study are commercially available as daily or extended wear. This study will investigate participants' wearing schedule intended for daily wear (NOT extended wear) similar to the average wearing time of 10-16 hours for daily wear lenses.

This study is considered to be a non-significant risk study based on United State Food and Drug administration (FDA) and International Standards Organization (ISO) guidelines because the study devices used as intended in this study (daily wear) don't represent a potential for serious risk to the health, safety or welfare of the subject, and (2) it is not an implant, (3) it is not used to support or sustain human life, (4) it is not of substantial importance in diagnosing, curing, mitigating or treating disease or otherwise prevents impairment of human health, (5) does not present a potential for serious risk to the health, safety or welfare of the subject (Appendix 2).

Complications that may occur during the wearing of contact lenses include discomfort, dryness, aching or itching eyes, excessive tearing, discharge, hyperemia and variable or blurred vision. More serious risks may include photophobia, iritis, corneal edema or eye infection. Although contact lens-related infections are very infrequent, the possibility does exist. The incidence of infection due to day-wear soft lenses is 0.035%. Almost always an infection will occur only in one eye. This risk is assumed by 35-million Americans who currently wear contact lenses.

Routine clinical procedures including auto-refraction, auto-keratometry, visual acuity, anterior ocular health assessment, and contact lens fitting will be used. In addition, high magnification imaging of the lens fit may be made using 35 mm or digital cameras, in vivo confocal microscopy, and/or specular microscopy. Patients will be monitored every two weeks until the end of the study to reduce if not eliminate the occurrence of adverse or potential adverse events. Patients will be given instructions from their ECP regarding early symptoms and signs of adverse events and their contact information.

## **8 Materials and Methods**

---

### **8.1 Participants**

---

Approximately 40 habitual soft contact lens wearers will be enrolled. Each subject will be required to attend up to five scheduled study visits over a period of approximately two months.

Each subject will be given a unique ID number. Additionally, all subjects must meet the study inclusion and exclusion criteria listed below.

#### **8.1.1 Inclusion criteria**

A person is eligible for inclusion in the study if he/she:

- Is between 18 and 40 years of age (inclusive)
- Has had a self-reported visual exam in the last two years
- Is an adapted soft contact lens wearer

- Has a contact lens spherical prescription between – 0.25 to – 8.00 (inclusive)
- Have no less than -0.75D of astigmatism in both eyes.
- Can achieve best corrected spectacle distance visual acuity of 20/25 (0.10 logMAR) or better in each eye.
- Can achieve a distance visual acuity of 20/30 (0.18 logMAR) or better in each eye with the study contact lenses.
- Has clear corneas and no active ocular disease
- Has read, understood and signed the information consent letter.
- Patient contact lens refraction should fit within the available parameters of the study lenses.
- Is willing to comply with the wear schedule (at least 5 days per week, > 8 hours/day assuming there are no contraindications for doing so).
- Is willing to comply with the visit schedule

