# 1 Introduction

---

According to a 2018 international contact lens prescribing report, silicone hydrogel materials accounted for 76% of soft lenses prescribed and for more than 90% of fits in some markets. In the US for 2018, silicone hydrogel lenses have a reported usage at 69% of fits. Data from Contact Lens Spectrum’s market research in the US showed that, across all contact lens designs, most of the reported fits and refits are with soft spherical contact lenses (49% versus 48% in 2017). CooperVision’s Avaira Vitality™ sphere lenses use a third generation silicone hydrogel material which makes the lens inherently wettable with no surface treatments, and uses naturally wettable building blocks to improve compatibility between silicone and hydrophilic domains. This, combined with the higher water content of Avaira Vitality™ ensures a high performing, comfortable lens.

Clariti Elite sphere lenses are part of a generation of silicone hydrogel portfolio from CooperVision which will be discontinued from the market in the near future. Therefore, CooperVision is interested in evaluating the clinical performance of existing wearers of Clariti Elite sphere lenses after a refit with Avaira Vitality™ silicone hydrogel sphere lenses over 4-weeks of daily wear.

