## 2 Study Objective

---

The aim of this prospective study is to evaluate the clinical performance of habitual wearers of Clariti Elite sphere lenses after a refit with Avaira Vitality sphere lenses for 4 weeks of daily wear.

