**The primary variables of interest are:**

- Lens fitting characteristics

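### The aim concerns habitual Clariti Elite wearers, but entry is open to any adapted soft-lens wearer, so the conclusion about the named population is not secured

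*Combined protocol and SAP*

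**What the plan says.** **Where Clariti Elite wearers are the population**

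- Section 1 explains that Clariti Elite belongs to a product line "which will be discontinued from the market in the near future", and that the sponsor is therefore interested in "evaluating the clinical performance of existing wearers of Clariti Elite sphere lenses after a refit".
- Section 2 makes this the objective: to "evaluate the clinical performance of habitual wearers of Clariti Elite sphere lenses after a refit with Avaira Vitality sphere lenses". The primary variable is "Lens fitting characteristics".
- Section 8.3.5 adds a preference question at Visit 5 and labels its two options as the habitual lens (Clariti Elite) and the test lens (Avaira Vitality).

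**Where they are not**

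- Section 8.1: "Approximately 40 habitual soft contact lens wearers will be enrolled".
- Section 8.1.1 asks of existing lens wear only that the person "Is an adapted soft contact lens wearer".
- Section 8.1.2 excludes on prescription, history of uncomfortable wear, acuity and ocular findings, and does not mention a brand.
- Section 10.1 puts all evaluated participants into the analysis and states no analysis by habitual lens.

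**Neutral on the point**

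- Section 3.1 states the hypotheses as a difference between the two study lenses and names no population.
- Section 4 describes the study as "comparing the fitting characteristics of Clariti Elite sphere lenses" with those of Avaira Vitality, and says that "the first pair of study lenses, (e.g. somofilcon A), will be dispensed and worn for 4-weeks" before the second pair is fitted. The visit headings in section 8.3 put Clariti Elite first.

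**The concern.** The study exists because one lens is leaving the market and the sponsor wants to know how its present wearers do on the replacement. Someone who has chosen and kept Clariti Elite may differ from someone who wears another brand and is handed Clariti Elite for four weeks. If the second kind of person can enter, and all results are pooled, the report can answer a question about habitual Clariti Elite wearers with data from people who are not.

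Two statements are at stake. One is the conclusion promised by the objective. The other is the reading of the Visit 5 preference as the subject's own lens against a new one: for a wearer of another brand, both options are lenses that the study assigned.

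**Working it through.** **1. Does any visible entry rule tie a subject to Clariti Elite?** The lens-related rules in sections 8.1.1 and 8.1.2 are:

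- adapted to soft lenses: no brand;
- lens power within a stated range and within the parameters in which the study lenses are made: this concerns what can be dispensed, not what is worn now;
- distance acuity with contact lenses, including with the study lenses: can be met by a wearer of any brand;
- willingness to keep to the wear schedule, and no history of failing to achieve comfortable wear: no brand.

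None requires current or past Clariti Elite wear, or a duration of it. The two lists show no blacked-out bullet, so redaction within them does not explain the gap. Section 8.2.1 then has all subjects trial fitted with both lenses. The visible text therefore permits any share of habitual Clariti Elite wearers, from none to all.

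**2. Does the lens comparison depend on habitual brand?** Under section 4 each subject wears Clariti Elite for four weeks and then Avaira Vitality for four weeks, and section 10.1 compares the lenses with paired tests. Each subject supplies both measurements whatever lens was worn before. Brand affects whom the result describes, not whether the comparison can be made.

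**3. Does the planned power depend on it?** Inputs from section 10.2: difference 1.0 point on a 0–10 scale, SD 1.9, alpha 0.05, 34 completers, 40 enrolled. Assumptions: SD 1.9 is the SD of within-subject differences, and the test is two-sided (sidedness is not stated).

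- Noncentrality = (difference / SD) × √n = (1.0 / 1.9) × √34 = 0.526 × 5.831 = 3.07, with 33 degrees of freedom.
- Power from the noncentral t distribution: 0.846, against the stated 84%. At n = 33 it is 0.834, so 34 is the smallest n that reaches 84%. A one-sided test would give 0.913, so the two-sided reading is the one that reproduces the plan.
- Allowance for loss: (40 − 34) / 40 = 15%.

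Habitual brand does not enter this calculation. Restricting entry to Clariti Elite wearers leaves it at 34 completers, 40 enrolled and 84.6% power.

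**4. Could the named group be recovered from a mixed sample?** The share is not given, so this is illustration only, using the same difference and SD within the subgroup. Of 34 completers, power for the habitual Clariti Elite subgroup alone would be 0.846 if all 34 belong to it, 0.73 for 26, 0.53 for 17 and 0.25 for 8. In a mixed sample, results by brand should be read as descriptive.

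**The case against.** The strongest reply is that this is a generalisability caveat and a label. The hypotheses in section 3.1 concern the two lenses and name no habitual-wearer population. By the time of the refit, every subject has just worn Clariti Elite for four weeks, so each is in a sense a current wearer, and habitual in section 8.3.5 may be loose wording for the first pair. The preference question can still be read as Clariti Elite against Avaira Vitality. The site may intend to recruit only Clariti Elite wearers, and the Visit 1 text, which cannot be seen, may contain a screening step or a record of the lens worn at entry.

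Much of this stands. The comparison of the lenses is sound in this respect, and the preference result keeps a meaning once the label is changed. But four assigned weeks do not make a wearer of another brand an established Clariti Elite wearer, and section 8.1 itself treats habitual wear as something subjects bring to enrolment. A rule hidden in the visit procedures would still leave the eligibility section at odds with the objective.

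A reader might go further and infer that the trial is biased or underpowered, that its type I error is inflated, or that the preference test loses power. The documents support none of these. Pairing and power do not involve brand, and a pooled result is correct for those enrolled. Any effect on the preference test would depend on the share of other-brand wearers and on their preferences. The plan gives neither, so not even the direction is known.

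**Conclusion.** The mismatch is real and can be read directly from sections 1, 2 and 8.3.5 set against sections 8.1, 8.1.1, 8.1.2 and 10.1. It should be fixed, because the group left unsecured is the one the study was set up to inform. Two things are not secured: the conclusion about habitual Clariti Elite wearers, and the word habitual in the preference question. The within-subject comparison and the 84% power are unaffected.

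No numerical size can be put on the consequence. The share of other-brand wearers is not given; if it is zero, the practical effect is nil. Confidence is high for the mismatch in the text and does not extend to any effect on the results. In particular, the text does not show that the wrong people will be enrolled, only that nothing visible prevents it.

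**What to change.** Choose one.

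**Option 1: restrict entry.** Add to section 8.1.1: *Currently wears clariti elite sphere as the habitual lens in both eyes*, with a minimum duration set by the sponsor. Change section 8.1 to *habitual clariti elite sphere wearers*. This is one inclusion line and one wording change, with no change to the sample size. The cost is a narrower recruitment pool at a single site.

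**Option 2: keep entry and restate the aim.** In both section 1 and section 2, describe the population as adapted soft-lens wearers refitted with Avaira Vitality after four weeks of Clariti Elite wear; changing section 2 alone would only move the contradiction. In section 8.3.5, label the preference options by study lens instead of calling one habitual. Record habitual brand at baseline and summarise results by it, descriptively. This needs no added subjects. The cost is a baseline item and a short summary, and a conclusion that no longer speaks specifically to habitual Clariti Elite wearers.

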### 8.1.2 Exclusion Criteria

A person will be excluded from the study if he/she:

- Has a CL prescription outside the range of the available parameters of the study lenses.
- Has a spectacle cylinder of  $\geq 1.00D$  in either eye.
- Has a history of not achieving comfortable CL wear (5 days per week; > 8 hours/day)
- Has contact lens best corrected distance vision worse than 20/25 (0.10 logMAR) in either eye.
- Presence of clinically significant (grade 2-4) anterior segment abnormalities
- Presence of ocular or systemic disease or need of medications which might interfere with contact lens wear.
- Slit lamp findings that would contraindicate contact lens wear such as:
  - Pathological dry eye or associated findings
  - Pterygium, pinguecula, or corneal scars within the visual axis
  - Neovascularization > 0.75 mm in from of the limbus
  - Giant papillary conjunctivitis (GCP) worse than grade 1
  - Anterior uveitis or iritis (past or present)
  - Seborrheic eczema, Seborrheic conjunctivitis
  - History of corneal ulcers or fungal infections
  - Poor personal hygiene
- Has a known history of corneal hypoesthesia (reduced corneal sensitivity)
- Has aphakia, keratoconus or a highly irregular cornea.
- Has Presbyopia or has dependence on spectacles for near work over the contact lenses.
- Has undergone corneal refractive surgery.
- Is participating in any other type of eye related clinical or research study.

## 8.2 Study Materials

---

### 8.2.1 Contact lens

All subjects will be trial fitted and, if suitable, dispensed the clariti® elite sphere and Avaira Vitality™ sphere lenses. The study lenses and solutions will be provided by the Sponsor. Details of the contact lenses are shown in Table 1.

**Table1: Study lenses**

	clariti® elite sphere	Avaira Vitality™ sphere
Manufacturer	CooperVision Inc.	CooperVision Inc.
Material	somofilcon A	fanfilcon A
WC %	56%	55%
Base Curve	8.6 mm	8.4 mm
Lens Diameter	14.2 mm	14.2 mm
Lens Power Sphere	- 0.25 to - 10.00	- 0.25 to - 10.00
Wearing schedule	Daily wear	Daily wear

### 8.2.2 Contact Lens care

OPTI-FREE® PureMoist® multipurpose disinfecting solution and lens cases (Alcon, Fort Worth, TX) will be provided to all subjects for care and maintenance of the contact lenses during the study.

### 8.2.3 Storage of Study Medications/Treatments

There are no unapproved investigational products used in this study requiring special storage accommodations.

### 8.2.4 Clinical Supply Inventory

There are no unapproved investigational products used in this study requiring special inventory requirements.

### 8.2.5 Disposal of Consumables

This study dispenses consumables (lenses) to participants for use during the study. Study lenses worn for 4-weeks of daily wear by participants will be collected at the last visit and destroyed.

### 8.2.6 Masking and Control of Study Materials

The study contact lenses will be **masked to the subject only**. Study lenses will be transferred, by an assistant, out of their packaging to unmarked new contact lens cases filled with unpreserved sterile saline just prior to dispensing to maintain subject masking of the study lenses.

- [REDACTED]
  - [REDACTED]
    - [REDACTED]
    - [REDACTED]
  - [REDACTED]
    - [REDACTED]
    - [REDACTED]
- Lens Fit
  - Lens centration (centered/slightly decentered/substantially decentered)
  - Corneal coverage [Y/N]
  - Post-blink movement (0 - 5 Likert scale)
  - Lens tightness. Push up test (0% to 100%, 50% optimum)
  - Overall fit acceptance (0 - 4) and reason if Grade 2 or less.
  - Remove study lenses and perform slit lamp examination
- [REDACTED]
  - [REDACTED]
    - [REDACTED]
    - [REDACTED]
    - [REDACTED]
    - [REDACTED]
    - [REDACTED]
  - [REDACTED]
    - [REDACTED]
    - [REDACTED]
    - [REDACTED]
    - [REDACTED]

Visit 3b: Dispense Avaira Vitality Lenses

The study subjects will undergo a trial fit in each eye with the second pair of study lenses.

- The performance of the second pair of study lenses should be assessed after 10 - 15 minutes settling time. The same variables as those collected on *visit 2, section 8.3.2* will be assessed.

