### 3.1 Study Hypothesis

---

- Null hypothesis ( $H_0$ ): There is no difference in lens performance between the study lenses for the key variables tested.
- Alternative hypothesis ( $H_1$ ): There is a difference in lens performance between the study lenses for the key variables tested.

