### 10.1 Statistical analysis

Summary statistics will be produced (e.g. mean, standard deviation). Differences between lenses will be compared using Paired t-tests. Paired t-tests / analysis of variance for normal (interval/continuous) data, Wilcoxon's signed ranks test for non-normal (ordinal) data, chi-squares test for nominal data. A binomial test will be used to evaluate lens preference questions. All participants who are evaluated will be used in the analysis. In the event of missing data, individual data points will be excluded in the analysis and not extrapolated from the collected data.

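### Push-up tightness is best at 50%, but the plan defines no measure of closeness to 50%, so testing the recorded score shows looser or tighter, not better or worse

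*Combined protocol and SAP*

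**What the plan says.** Section 2 names one visible primary variable, "Lens fitting characteristics", and section 4 describes the study as "comparing the fitting characteristics of Clariti Elite sphere lenses" with those of Avaira Vitality. The null hypothesis in section 3.1 is that "There is no difference in lens performance between the study lenses for the key variables tested".

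The Lens Fit list belongs to the visit procedures of section 8.3, although in the public text it follows section 8.2.6. It has five visible assessments: centration, corneal coverage, post-blink movement, tightness and overall fit. Tightness is recorded as "Lens tightness. Push up test (0% to 100%, 50% optimum". Overall fit is a separate grade: "Overall fit acceptance (0 - 4) and reason if Grade 2 or less".

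Section 10.1 shows no redaction. It says "Differences between lenses will be compared using Paired t-tests" and then assigns tests by data type: "Paired t-tests / analysis of variance for normal (interval/continuous) data", Wilcoxon signed-rank for ordinal or non-normal data, chi-square for nominal data, and a binomial test for preference. On description it says "Summary statistics will be produced (e.g. mean, standard deviation"). It does not name tightness, define a distance from 50% or an acceptable band around it, or say how a tightness difference is to be read.

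**The concern.** On a scale with its optimum in the middle, a difference in the recorded score has no fixed meaning for quality. A rise of 10 points is an improvement from 40% to 50% and a deterioration from 50% to 60%. A paired test on the recorded score treats the two alike.

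Two misreadings follow:

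- If the lenses sit on opposite sides of 50%, a significant raw difference can be taken as a difference in performance when both are equally far from the optimum.
- If they differ mainly in spread, loose and tight fits cancel in the mean. A non-significant result can then be taken as equal performance when one lens misses the optimum by more.

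A shift in tightness is plausible here: Table 1 gives base curves of 8.6 mm and 8.4 mm at the same 14.2 mm diameter. That supports a shift only; it says nothing about unequal spread.

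**Working it through.** **The plan's own figure.** Section 10.2 gives SD 1.9, difference 1.0, alpha 0.05 and 34 subjects for 84% power. Taking 1.9 as the SD of paired differences and a two-sided test, the noncentrality is (1.0/1.9) × √34 = 3.07 and the critical value is t(33) = 2.03, which gives 84.6% power. The figure reproduces. It is for a 0–10 scale, not the 0–100% push-up scale, so only n = 34 and the paired, two-sided 0.05 test carry over.

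**Assumptions.** The documents give no tightness means, SDs or correlation. I assumed normal scores rounded to 5% steps within 0–100 and a within-subject correlation of 0.3 to 0.7, with 20,000 simulated trials per scenario.

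**Variables compared for each subject.**
- Raw: d = score(Avaira Vitality) − score(Clariti Elite)
- Distance: D = |score(Avaira Vitality) − 50| − |score(Clariti Elite) − 50|

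Each is tested by t = mean / (SD/√34).

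**Check of the raw test by formula.** At correlation 0.5 and SD 10 for both lenses, the SD of d is 10 × √(2 × (1 − 0.5)) = 10. For 45% against 55%, the noncentrality is (10/10) × √34 = 5.83 and the power is about 100%, as simulated.

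**Rejection rates** (ranges cover correlation 0.3 to 0.7)

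| Lens means | SDs | Raw score | Distance from 50 |
|---|---|---|---|
| 45 vs 55 | 10, 10 | about 100% | 5% |
| 50 vs 50 | 10, 20 | 5% | 95–99% |
| 50 vs 50 | 5, 10 | 5% | 93–99% |
| 50 vs 50 | 10, 15 | 5% | 57–75% |
| 55 vs 60 | 5, 5 | 99–100% | 99–100% |
| 50 vs 55 | 10, 10 | 66–94% | 10–11% |
| 55 vs 60 | 10, 10 | 65–94% | 35–53% |

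**Reading the table.**
- In row 1 the mean distance from 50% is 8.9 points for both lenses, so the raw rejections say nothing about which is nearer the optimum.
- In row 2 the mean distance doubles (7.9 against 15.8) and the raw test does not see it. In row 3 it is 3.8 against 7.9, with the same result.
- In row 5 both lenses lie on one side of 50% with small spread, and the two tests agree.
- In rows 6 and 7 the raw test is the more sensitive, so distance should not replace it.

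The Wilcoxon signed-rank test gives the same pattern at correlation 0.5 (4,000 trials): row 1, 100% raw and 5% distance; row 2, 4% and 96%; row 6, 79% and 10%.

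**Order of averaging.** Eyes scored 40% and 60% average to 50%, and the distance of that average is 0. The average of the two distances is (10 + 10)/2 = 10. Distance must be computed per eye first.

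**The case against.** The strongest reply is that the plan answers the question it asks. It compares fitting characteristics, its alternative is non-directional, and a raw paired comparison is a valid test that a characteristic differs. Section 10.1 never says the recorded tightness score is the analysed variable, so the criticised test is inferred. The 50% optimum is written into the item, means and SDs will be reported, and the 0–4 overall grade judges fit quality directly. The distributions above are assumed, and fitting both lenses before dispensing should limit gross misfits. Finally, |score − 50| treats loose and tight errors as equally bad, which the protocol does not say, and it adds a test on a primary component.

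Much of this stands, and it limits the point:

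- The raw test is valid for a shift and should stay. But the hypothesis is worded as performance, and no visible text links a tightness difference to it.
- Section 10.1 is silent on tightness, but its general rule applied to a recorded percentage leads to the raw comparison.
- Summary statistics and the overall grade help a careful reader. Neither is a test of closeness to 50%.
- Screening weakens the unequal-spread cases. If scores outside 30–70% never occur (an assumption; correlation 0.5), the distance test's rejection rate falls from 97% to 55% for SDs 10 and 20, and from 63% to 31% for SDs 10 and 15. For SDs 5 and 10 it stays at about 94%, and the 45% against 55% case is unchanged.
- The symmetry of |score − 50| and the additional test are real costs, and are acknowledged in the fix.

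Scoring instructions may exist in redacted visit text or appendices. Section 10.1 itself is unredacted, so this tempers confidence only.

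**Conclusion.** The concern holds. The protocol states an interior optimum for a component of its primary variable, and the analysis section has no variable that measures distance from it. Following section 10.1 as written tests whether one lens is looser or tighter than the other, and leaves the performance question for this item unanswered.

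The consequence depends on distributions the documents do not give. It ranges from nothing (both lenses on the same side of 50%, small spread) to a result that misleads almost every time (means on opposite sides of 50%). The straddling case is robust to the assumptions tried; the unequal-spread cases are less so. This should be corrected because the correction is cheap. It affects one of five visible fit items and does not touch the sample-size calculation.

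**What to change.** In section 10.1:

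1. Define |score − 50| as the tightness performance variable. Compute it for each eye, then average the two eyes, and compare lenses by paired t-test or Wilcoxon signed-rank test.
2. Keep the comparison of recorded scores as a test of a shift in fit, looser or tighter.
3. State that a raw difference alone is not to be read as better or worse performance, and that its absence is not to be read as equal performance.

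The cost is one derived variable, one additional test and two sentences of interpretation; no new data are collected. The derived variable weights loose and tight errors equally and is less sensitive to a consistent shift, which is why the raw comparison stays. The fix uses only the optimum the protocol already states.
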